## 14. STUDY TREATMENT COMPLIANCE

Compliance with the use of study treatment will be presented for the SAF population. The intake of study treatment will be recorded daily in the e-Diary. The e-Diary will be the primary source for the calculation of compliance with the use of study treatment.

Non-compliance to study treatment intake within a cycle is defined as 4 or more days with forgotten tablets, or 2 or more consecutive days with forgotten tablets.

- Overall Compliance to study treatment will be calculated as following:

$$\frac{\text{Number of days that at least one tablet was taken in the treatment period, as per e-Diary}}{[\text{Date of last dose} - \text{date of first dose} + 1]} \times 100$$

In addition, the number and percentage of participants who took 3 or more tablets on a given day, which is considered as an overdose, will be presented. Number of participants (and cycles) with evaluable cycles will be tabulated and listed.

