6.0 STUDY TREATMENT

Study treatment is defined as any investigational treatment(s), marketed product(s), placebo, or medical device(s) intended to be administered to a participant according to the study protocol.

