6.4.2 Management of Missed NOMAC-E2 Tablets

The NOMAC-E2 blister contains 28 tablets: 24 white tablets with the active substances (number 1 to 24) and 4 yellow tablets without active substances (number 25 to 28).

The participant should take one tablet every day at about the same time, without regard to meals and with some liquid if needed and in the order directed on the blister. Stickers marked with the 7 days of the week are provided; the participant should choose the sticker that starts with the day the participant begins taking the study drug.

If a participant misses a dose, the risk of pregnancy increases; this includes starting the pack late. The more tablets missed and the closer the missed tablets are to the 4 yellow placebo tablets, the higher the risk of a pregnancy.

The following advice **applies in case of** missed white active tablets:

1 active white tablet missed

The user should take the last missed tablet as soon as she remembers, even if this means taking 2 tablets at the same time. She then continues to take tablets at her usual time. She does not need any additional contraceptive protection.

2 or more active white tablets missed

The user should take the last missed tablet as soon as she remembers, even if this means taking 2 tablets at the same time. She then continues to take tablets at her usual time. A condom should be used until she has completed 7 days of uninterrupted white active tablet intake. This might continue into the next cycle. If intercourse took place in the preceding 7 days, the possibility of a pregnancy should be considered. The more tablets are missed and the closer to the regular placebo tablet interval, the higher the risk of a pregnancy.

Finally, if the participant is not sure what to do about what advice to follow on the number of tablets missed, she should be advised to use a barrier method anytime. If the woman missed active white tablets and subsequently has no withdrawal bleed in the first normal placebo tablet interval, the possibility of a pregnancy should be considered.

If yellow placebo tablets are missed contraceptive protection is not reduced. Yellow tablets from the last (4th) row of the blister can be disregarded. However, the missed tablets should be discarded to avoid unintentionally prolonging the placebo tablet phase.

The following advice **applies in case of** GI disturbances:

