8.2.3.2 Study Treatment Compliance

The prescribed dosage and mode of administration may not be changed.

The intake of study drug will be recorded by the study participants daily in the e-Diary. The e-Diary data will be the primary source to measure study treatment compliance. Any deviations from the prescribed dosing regimen will be captured in the e-Diary.

During both on-site and phone visits, compliance will be reviewed by the site using the e-Diary data. Participants exhibiting poor study drug intake compliance should be counseled on the

importance of good compliance to the study drug dosing regimen. These compliance checks by the site and the counseling on the importance of compliance to study drug intake must be documented by site personnel in the source documents.

Non-compliance to study drug intake during the scheduled active cycle period (Days 1 to 24) is defined as 4 or more days with forgotten tablets, or 2 or more consecutive days with forgotten tablets. The remaining treatment cycles will be included in the Per-Protocol (PP) analysis unless excluded by other protocol deviations (see Section 9.3.4 for more information).

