9.3.4 Per-Protocol Analysis and Protocol Deviations

A protocol deviation is any change, divergence, or departure from the study design or procedures defined in an approved protocol.

The final determination of important or non-important protocol deviations, and thereby the composition of important deviations which would exclude participants or time periods from an associated PP population, will be made prior to the final database lock and will be documented in a separate memo. These deviations may include, but are not limited to, the presence of any of the following:

- Treatment cycles in which the participant is non-compliant with study drug will be excluded. Non-compliance to tablet intake during the scheduled active cycle period (Days 1 to 24) is defined as either:
 - 4 or more days with forgotten tablets, or
 - 2 or more consecutive days with forgotten tablets.
- Participant has >75% of treatment cycles in which either the participant was not considered at risk for pregnancy or was non-compliant with study drug or e-Diary completion will exclude the participant from the PP 1 set.
- Treatment cycles from participant having used prohibited medication listed in [Table 6](#). Treatment cycles will be excluded in which the medication was used, including treatment cycles started within 28 days after discontinuation of prohibited medication. The remaining treatment cycles of the participant will be included in the PP analysis unless excluded by other protocol deviations.

Note: Treatment cycles in which hormonal contraception other than the NOMAC-E2 COC has been used are considered a protocol deviation for the purposes of the CCA or RPA, and to be excluded from the FAS evaluable. Such treatment cycles have already been excluded from the contraceptive efficacy calculation in the rFAS. Treatment cycles in which condoms (or other non-hormonal methods of back-up contraception) are used will be considered in the CCA and RPA, in contrast to the contraceptive efficacy analysis, as such use is not expected to affect the CCA and RPA outcomes.

- Participant is pregnant or has taken study drug without a documented negative pregnancy test, on the day of first study drug intake.
- Participant has undiagnosed (unexplained) abnormal vaginal bleeding or any other abnormal bleeding that meets exclusion criteria at screening as being attributable to underlying pathology

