## MODIFICATION HISTORY

Unique Identifier for this Version	Date of the Document Version	Author	Significant Changes from Previous Authorized Version
Version 1.0	02 Dec 2023	[REDACTED]	Initial version
Version 2.0	23 Apr 2024	[REDACTED]	
Updated following TLFs per Organon team review.
 

• Updated Table 14.1.1.1 Participant Disposition, clarified the calculation of percentages.

• Removed Tables 14.3.4.1 Markedly abnormal lab test.

• Added Tables 14.3.4.1 through 14.3.4.3 Actual and change from baseline in lab tests by visit in hematology, chemistry, and urinalysis.

• Added Listing 14.3.5.1 Markedly Abnormal liver function tests.

• Corrected/updated Section 16 Appendix A.

• Changed the definition of treatment compliance in Table 14.1.7.1.

• Just keep two visits of baseline and last measurement and remove other visits in

---

Document:

[REDACTED]

Author:

[REDACTED]

Version Number:

2.0

Version Date:

23APR2024

Template No.: CS\_TP\_BS016 Revision 6

Reference: CS\_WI\_BS005

Effective Date: 02Dec2019

Copyright © 2009, 2010, 2012, 2016, 2018, 2019 [REDACTED] All rights reserved. The contents of this document are confidential and proprietary to [REDACTED] and its subsidiaries. Unauthorized use, disclosure or reproduction is strictly prohibited.

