### 1.1. IMPORTANT DEFINITIONS

**Treatment cycle:** A treatment cycle is defined by the period between 2 start dates of a blister, as recorded in the participant's e-Diary.

**Evaluable cycle (at risk):** cycles with duration 22 to 35 days (inclusive) with affirmed heterosexual vaginal intercourse and lack of additional contraception use. In cases of a confirmed pregnancy, cycles that start after the estimated date of conception (as determined by the investigator based on gestational age from an ultrasound) will not be considered "at risk".

**On-treatment period for pregnancies:** the period from the first date of intake of study treatment up to and including 7 days after the last date of study treatment intake.

- **Pre-treatment pregnancies:** pregnancies with an estimated date of conception before the first date of study treatment intake. Also, all pregnancies in participants in which all dispensed trial treatment is returned unused (per investigator's record) will be considered pre-treatment.
- **On-treatment pregnancies:** On-treatment pregnancies are pregnancies with an estimated date of conception between the first date of intake of study treatment up to and including 7 days after the last date of study treatment. In the absence of an ultrasound, the earliest positive serum/urine test date will be utilized to classify pregnancy category. In this case, an on-treatment pregnancy is defined as a positive serum/urine pregnancy test date that is more than 7 days after the first pill and not more than 14 days after the last pill.
- **Post-treatment pregnancies:** Post-treatment pregnancies are pregnancies with an estimated date of conception after the on-treatment period as defined above. In the absence of ultrasound results, post-treatment pregnancy is defined as a positive serum/urine pregnancy test date that is more than 14 days after the last pill.

Final determination for pre/during/post treatment will be made by the clinical team.

Document: [REDACTED]

Author: [REDACTED]

Version Number:

2.0

Version Date:

23APR2024

Template No.: CS\_TP\_BS016 Revision 6

Reference: CS\_WI\_BS005

Effective Date: 02Dec2019

Copyright © 2009, 2010, 2012, 2016, 2018, 2019 [REDACTED]. All rights reserved. The contents of this document are confidential and proprietary to [REDACTED] and its subsidiaries. Unauthorized use, disclosure or reproduction is strictly prohibited.

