## 8. OUTPUT PRESENTATIONS

Conventions for presentation of data in outputs will be included in the Programming Conventions for Outputs document.

The templates provided with this SAP describe the presentations for this study and therefore the format and content of the summary tables, figures, and listings to be provided by [REDACTED] Biostatistics.

All data will be listed, and summary tables will be provided. Continuous variables will be summarized for the measured values and change from baseline values using the number of observations, mean, standard deviation, median, minimum, and maximum. Categorical variables will be summarized with counts and percentages for each category.

---

Document: [REDACTED]

Author: [REDACTED]

Version Number:

2.0

Version Date:

23APR2024

Template No.: CS\_TP\_BS016 Revision 6

Reference: CS\_WI\_BS005

Effective Date: 02Dec2019

Copyright © 2009, 2010, 2012, 2016, 2018, 2019 [REDACTED]. All rights reserved. The contents of this document are confidential and proprietary to [REDACTED] and its subsidiaries. Unauthorized use, disclosure or reproduction is strictly prohibited.

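### SAP Section 14 drops the protocol's Days 1 to 24 limit from the per-cycle non-compliance rule without declaring it, so two adjacent missed placebo days make a cycle non-compliant

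*SAP*

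**What the plan says.** The protocol gives the rule twice, each time limited to the active tablets. Section 8.2.3.2 opens with "Non-compliance to study drug intake during the scheduled active cycle period (Days 1 to 24" and Section 9.3.4 with "Non-compliance to tablet intake during the scheduled active cycle period (Days 1 to 24) is defined as either". Both set the same two limbs: at least 4 days with forgotten tablets, or at least 2 such days in a row.

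SAP Section 14 keeps both limbs and changes the day range: "Non-compliance to study treatment intake within a cycle is defined as 4 or more days with forgotten tablets", with the consecutive-day limb following in the same sentence.

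Four other places fix what that range covers:

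- SAP Section 1.1: "A treatment cycle is defined by the period between 2 start dates of a blister".
- SAP Section 3.1: a cycle is 24 active days followed by 4 placebo days.
- Protocol Section 6.0: "Study treatment is defined as any investigational treatment(s), marketed product(s), placebo, or medical device(s", so placebo belongs to study treatment.
- Protocol Section 6.4.2, on missed placebo tablets: "Yellow tablets from the last (4th) row of the blister can be disregarded".

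SAP Section 3.2, which lists changes from the protocol, covers the safety-only scope, the analysis sets and a correction to a visit-window footnote. It does not mention compliance. The only related trace is the Version 2.0 entry in the SAP modification history: "Changed the definition of treatment compliance in Table 14.1.7.1". Protocol Section 9.4 gives the SAP precedence where the two documents differ.

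**The concern.** The two documents share thresholds but not a day range, so one label covers two different measures. Under the protocol, a non-compliant cycle means missed active tablets. Under the SAP as written, it can also mean that every active tablet was taken and some placebo tablets were not, which the protocol's own advice treats as of no consequence.

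A summary of non-compliant cycles built on the SAP wording would mix the two and could overstate poor adherence to the active drug. A reader comparing it with the protocol would see familiar thresholds and no sign that the rule had widened. Because the SAP prevails, the wider rule would govern by default rather than by a recorded decision.

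**Working it through.** The plan gives no figure to reproduce here. The check applies both rules as written to the same cycles.

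**Inputs**

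- Thresholds (protocol 8.2.3.2 and 9.3.4; SAP 14): flag a cycle if forgotten days total at least 4, or if any 2 adjacent days are both forgotten.
- Day range: Days 1 to 24 under the protocol; the whole cycle under the SAP.
- Cycle (SAP 3.1): 24 active days plus 4 placebo days, 28 in all.

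**Step 1: all active tablets taken.** Each of Days 25 to 28 is either taken or missed, giving 2^4 = 16 patterns. The protocol rule sees 0 forgotten days in every one.

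| Placebo days missed | Patterns | Flagged by SAP wording | Flagged by protocol |
|---|---|---|---|
| 0 | 1 | 0 | 0 |
| 1 | 4 | 0 | 0 |
| 2 | 6 | 3 (adjacent pairs: 25–26, 26–27, 27–28) | 0 |
| 3 | 4 | 4 | 0 |
| 4 | 1 | 1 | 0 |
| Total | 16 | 8 | 0 |

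One missed placebo tablet alone never triggers the flag. With only Days 25 and 26 missed, the cycle is non-compliant under the SAP although tablets were taken on 26/28 = 92.9% of days. With all four missed, both limbs are met, at 24/28 = 85.7%.

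**Step 2: mixed cycles.** The classification can also change when some active tablets are missed.

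- Days 24 and 25 missed: the protocol counts one forgotten day (not flagged); the SAP counts two consecutive days (flagged).
- Three isolated active days plus one placebo day missed: the protocol counts 3 (not flagged); the SAP counts 4 (flagged).

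**Step 3: early start of the next blister.** If all active tablets and no placebo tablets are taken, a cycle of length L has L − 24 forgotten days, all consecutive. L = 24 or 25 gives 0 or 1 and is not flagged. L = 26, 27 or 28 gives 2, 3 or 4 and is flagged. The SAP result then depends on when the next blister was opened, not on active tablet intake.

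**Step 4: illustration of frequency.** The documents give no rate. Assume that each placebo day is missed independently with probability q and that no active tablet is missed. From the table, the probability of a flag is 3q²(1−q)² + 4q³(1−q) + q⁴.

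| q (assumed) | Cycles flagged by SAP wording |
|---|---|
| 5% | 0.7% |
| 10% | 2.8% |
| 20% | 10.4% |
| 30% | 21.6% |

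For q = 10%: 0.0243 + 0.0036 + 0.0001 = 0.028. Under these assumptions the protocol rule flags 0% throughout. Independence is a simplification: a participant who drops the whole placebo row misses adjacent days by construction.

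**The case against.** The strongest objection is that no visible output uses the sentence. SAP Section 14 names an overall compliance percentage with its own formula, a count of participants taking 3 or more tablets on a day, and a tabulation of evaluable cycles. Evaluable cycles are defined in SAP Section 1.1 without reference to tablet intake. The per-protocol use of the rule went when the efficacy analyses were dropped, and SAP Section 3.2 declares that. SAP Section 8 adds: "The templates provided with this SAP describe the presentations for this study and therefore the format and content of the summary tables". Those templates are not visible, so a day limit in Table 14.1.7.1 cannot be ruled out. This stands as a limit on the consequence. It does not remove the discrepancy: Section 14 says compliance will be presented and sets this rule beside a separately labelled overall measure, so it reads as a rule for output. If the table shell does carry the limit, the SAP text disagrees with its own shell.

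A second objection is that a placebo tablet left out on purpose is not forgotten. However, the protocol uses the same word and still adds Days 1 to 24 both times, so the word does not carry the limit by itself. The SAP also gives no rule for coding such days.

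A third objection is that the overall compliance formula counts every day from first to last dose, placebo days included, so the wider cycle rule is at least consistent within Section 14. That is fair. Restoring the limit leaves two day bases in one section, which is acceptable if each is labelled. If consistency was the reason for widening the rule, it should be stated.

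Finally, all data will be listed, so active and placebo misses could be separated from the listings. That is true of the data, but not of a summary count of non-compliant cycles.

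**Conclusion.** The concern holds, at minor severity. SAP Section 14 widens the protocol's rule from Days 1 to 24 to the whole cycle, and neither SAP Section 3.2 nor the modification history declares it as a departure from the protocol. In a 28-day cycle with all active tablets taken, 8 of 16 placebo patterns are flagged instead of 0 of 16.

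This rests on reading the cycle as SAP Section 1.1 defines it and on treating an untaken placebo tablet as forgotten. The wording difference is certain. Its effect on reported results is conditional on the unseen templates and cannot be sized without a rate of placebo skipping. At most it reaches descriptive compliance output for the safety set. It does not touch any analysis set, the adverse event analyses or the classification of pregnancies.

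**What to change.** In SAP Section 14, limit the per-cycle rule to the scheduled active period, Days 1 to 24, as in protocol Sections 8.2.3.2 and 9.3.4. Confirm that Table 14.1.7.1 uses the same range, and label the overall percentage as covering all tablet days. If the wider range was intended, list it with a reason in SAP Section 3.2 and say how untaken placebo tablets are coded.

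The cost is one phrase in Section 14 and a check of one table shell. Cycle day can be derived from the blister start dates in the e-Diary, so no new data are needed.

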## 15. SAFETY OUTCOMES

All outputs for safety outcomes will be based on the SAF population.

### 15.1. ADVERSE EVENTS

AEs will be coded using MedDRA coding dictionary, Version 26.1 or higher.

Treatment-emergent adverse events (TEAEs) are defined as AEs that started on or after the day of first dose of study treatment (or worsened in severity) and prior to the last date of study treatment + 14 days (inclusive). See Appendix A for handling of partial dates for AEs. In the case where it is not possible to define an AE as treatment emergent or not due to a partial start date, the AE will be classified by the worst case; i.e. treatment emergent. Pre-treatment AEs/SAEs starting before the on-treatment period, including those starting on the day of first dose of study treatment yet prior to the study treatment intake, will be excluded from the TEAE analyses. Pre- and post-treatment AEs will be identified in listings.

---

Document: [REDACTED]

Author: [REDACTED]

Version Number:

2.0

Version Date:

23APR2024

Template No.: CS\_TP\_BS016 Revision 6

Reference: CS\_WI\_BS005

Effective Date: 02Dec2019

Copyright © 2009, 2010, 2012, 2016, 2018, 2019 [REDACTED]. All rights reserved. The contents of this document are confidential and proprietary to [REDACTED] and its subsidiaries. Unauthorized use, disclosure or reproduction is strictly prohibited.

An overview table of number (%) of participants within each of the categories described in the sub-section below will be provided as specified in the templates. The broad AE categories consisting of the percentage of participants with any TEAE, a drug-related TEAE, a serious TEAE, a TEAE that is both drug-related and serious, and a TEAE leading to discontinuation of study treatment will be summarized. Similar Table by BMI group ( $<30 \text{ kg/m}^2$ ,  $\geq 30 \text{ kg/m}^2$ ) will be provided. Listings will include all AEs (including participants who enrolled more than once).

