For continuous measures such as changes from baseline in laboratory tests and vital sign parameters, summary statistics for on-treatment values will be provided in table format at V2 and V7.

For summary statistics of laboratory parameters and vital signs per visit, visit windows as described in [Table 11](#) will be used.

Table 11 Timeframe Used in the Analysis of Vital Signs and Laboratory Parameters

Definition	Visit	Visit window (treatment day)
Baseline	V1 Screening	<1
In-treatment ^a	V3 After Cycle 1	29 \pm 28 days
	V4 After Cycle 4	113 \pm 28 days
	V5 After Cycle 7	197 \pm 28 days
	V6 After Cycle 10	281 \pm 28 days
	V7 After Cycle 13	379 \pm 28 days
	Last measurement	>1

Abbreviation: V=Visit

a. From Day 1 until ≤ 28 days after last tablet intake; Day 1 is defined as day of first study drug intake

Values outside these visit windows, or outside the defined in-treatment period for post-baseline assessments, will be excluded from the analysis of that particular visit.

However, these visit windows will only be applied for analyses performed per visit; no values will be excluded from the determination of markedly abnormal laboratory or vital signs values

(unless outside the defined in-treatment period). If more than one observation is available within a specific visit window, the latest value will be used for analysis.

9.4.3.1 *Adverse Events*

An overview table of the number (percentage) of participants with any AEs, SAE, drug-related AEs, any serious drug-related AEs, any discontinuation due to AE, any discontinuation due to a SAE, any discontinuation due to a drug-related AE, any discontinuation due to serious drug-related AE, and any deaths will be presented for the on-treatment period. Pre-treatment AEs/SAEs starting before the in-treatment period will be excluded from the AE analyses (unless there is an increase in Investigator assessed intensity or causality, or the AE meets SAE criteria post-treatment allocation) and reported in separate frequency tables with the methods described above.

The number (percentage) of participants with at least one AE will be presented in a frequency table of Medical Dictionary for Regulatory Activities (MedDRA) system organ class (according to the primary path) and MedDRA preferred term. The same tables will be presented by relationship to study drug (“Related” and “Not related”) by the Investigator; and by severity of the AE (“mild”, “moderate”, “severe”).

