## 6.2. BASELINE

Unless otherwise specified, baseline is defined as the last non-missing measurement taken prior to reference start date (including unscheduled assessments). In the case where the last non-missing measurement and the reference start date coincide, that measurement will be considered pre-baseline with the following exceptions:

Adverse events (AEs) and medications commencing on the reference start date will be considered as either pre-baseline or post-baseline based on the collected eCRF assessment of whether the item started prior to the start of study treatment.

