## 16. APPENDIX A

### 16.1. ALGORITHM FOR TREATMENT EMERGENCE OF ADVERSE EVENTS:

---

Document:

Author:

Version Number:

2.0

Version Date:

23APR2024

Template No.: CS\_TP\_BS016 Revision 6

Reference: CS\_WI\_BS005

Effective Date: 02Dec2019

Copyright © 2009, 2010, 2012, 2016, 2018, 2019 [REDACTED]. All rights reserved. The contents of this document are confidential and proprietary to [REDACTED] and its subsidiaries. Unauthorized use, disclosure or reproduction is strictly prohibited.

AE START DATE	AE STOP DATE	ACTION
Known	Known/Partial/ Missing	
If AE stop date is partial, impute AE stop date as latest possible date (i.e., last day of month if day unknown or 31st December if day and month are unknown).
 
If AE start date < study treatment start date, assign as pre-treatment AE.
 
If AE start date >= study treatment start date and <= study treatment stop date + 14 days, assign as TEAE.
 
If AE start date > study treatment stop date + 14 days, assign as post-treatment AE.

Partial	Known/Partial/ Missing	
If AE stop date is partial, impute AE stop date as latest possible date (i.e., last day of month if day unknown or 31st December if day and month are unknown).
 
Impute AE start date as the study treatment start date, if:
 

the year of the AE start date is equal to the year of the study treatment start date and the AE stop date is later or equal to the study treatment start date or is missing.

the year and month of the AE start date is equal to the year and month of the study treatment start date and the AE stop date is later or equal to the study treatment start date or is missing.

 
Otherwise, Impute AE start date as earliest possible date (i.e. first day of month if day unknown or 1st January if day and month are unknown). Then:
 
If AE start date < study treatment start date, assign as pre-treatment AE.
 
If AE start date >= study treatment start date and <= study treatment stop date + 14 days, assign as TEAE.
 
If AE start date > study treatment stop date + 14 days, assign as post-treatment AE.

Document: [REDACTED]

Author: [REDACTED]

Version Number:

2.0

Version Date:

23APR2024

Template No.: CS\_TP\_BS016 Revision 6

Reference: CS\_WI\_BS005

Effective Date: 02Dec2019

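### SAP 16.1 classes known-date adverse events by calendar date alone, against 15.1 and 6.2 for Day 1 events before the first tablet, and it has no branch for events that worsen

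*SAP*

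**What the plan says.** **SAP 15.1** defines a TEAE by onset from the day of first dose up to 14 days after the last dose, and adds the clause "or worsened in severity". A later sentence in the same section excludes pre-treatment events from the TEAE analyses, "including those starting on the day of first dose of study treatment yet prior to the study treatment intake". That sentence does not repeat the worsening clause.

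**SAP 6.2** says that events commencing on the reference start date are placed before or after baseline "based on the collected eCRF assessment of whether the item started prior to the start of study treatment". The item needed to order a Day 1 event is therefore collected.

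**SAP 16.1** is titled as the algorithm for treatment emergence. Its first row covers known start dates: "If AE start date < study treatment start date, assign as pre-treatment AE". A start on or after the treatment start date, up to 14 days after the stop date, is a TEAE. Neither this row nor the rows for partial or missing start dates mention the eCRF item or a change in severity.

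**Protocol 9.4.3.1** excludes events that start before treatment "unless there is an increase in Investigator assessed intensity or causality", or unless the event becomes serious after treatment allocation.

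**SAP 3.2**, which lists departures from the protocol, does not mention any of this.

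**The concern.** Following 16.1 literally gives a result that 15.1 says is wrong, and the SAP states no order of precedence between the two. A Day 1 event before the first tablet would be counted as treatment-emergent, which overstates the incidence. A pre-treatment event that intensifies on treatment could be left out, which understates it.

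The study ended early, and the SAP analyses safety only. The TEAE classification feeds the overview table and its BMI-group version, and the tables by organ class, severity, relationship, seriousness, discontinuation and events of clinical interest. An ambiguity here reaches most of what will be reported. The SAP history records that Appendix A was corrected in version 2.0, and the mismatch is still in that version.

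**Working it through.** The point involves no sample size, power or interval figure, and the plan states no figure to reproduce. The check is to trace two events with fully known dates through each rule.

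| Event | SAP 15.1 | SAP 6.2 | SAP 16.1, known start date | Protocol 9.4.3.1 |
|---|---|---|---|---|
| A. Starts on the first-dose date, before the first tablet | Not a TEAE (exclusion sentence) | Decided by the eCRF item: before treatment | Start date = treatment start date, so TEAE | Does not address same-day order |
| B. Starts before the first-dose date, severity increases on treatment | TEAE by the worsening clause; the exclusion sentence is silent on it | Not applicable | Start date < treatment start date, so pre-treatment | Not excluded (increased intensity) |

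**Event A.** 15.1 and 6.2 agree, and 16.1 gives the opposite answer. The first sentence of 15.1 alone would make every Day 1 event a TEAE, but its exclusion sentence narrows that. Only 16.1 is left out of step.

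**Event B.** 16.1 disagrees with the 15.1 definition and with the protocol. Whether such a record exists depends on how a worsening is entered, and the documents point both ways. Protocol Appendix 4 treats exacerbation of a pre-existing condition as an adverse event and requires each event to be recorded separately. That could give a new record with an on-treatment start date, which 16.1 already classes correctly. The follow-up part of the same appendix sends new or updated information to the form completed originally. That would keep the pre-treatment start date, and 16.1 would then class the event as pre-treatment.

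**How many events.** The documents give no counts. For the pool behind event B, Protocol Table 8 has events before first intake reported only if they are due to a protocol procedure or cause exclusion, while the text of Protocol 8.4.1 calls for all events from consent onwards. The pool is narrow under the table and wider under the text.

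**Effect on the overall proportion.** A participant counts once, so a reclassified event changes the overall TEAE proportion only if it was her only TEAE. Each such participant moves it by 100/N percentage points, where N is the number treated. At the planned 1,878 allocated participants this is 100/1,878 = 0.05 points. N is not in the documents. If early termination made it smaller, the step is larger in proportion. The relative effect can be greater for a single preferred term with few cases.

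**The case against.** The best defence is that Appendix A only handles dates. SAP 15.1 refers to it for partial dates and SAP 7.1 for partial or missing ones. On that view the definition lies in 15.1, and a specific Day 1 rule stated in two sections prevails over a general date row. This has force: nothing in the SAP says that 16.1 is the rule to be programmed, and a careful programmer might well apply 6.2. It does not remove the conflict, because 16.1 is titled as the treatment-emergence algorithm, has its own row for known dates, and contradicts 15.1 there.

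On worsening, the defence is that an exacerbation is a new event, and that the two sentences of 15.1 can be read together, with the exclusion covering events that are only pre-treatment. Both readings are possible. The instruction to update the original form leaves the first unsettled, and the second does not give 16.1 a worsening branch.

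The defence is right on impact. The trial is single-arm with no statistical testing, the output is a synoptic report, and the listings show all events with pre- and post-treatment ones identified, so no event disappears. SAP Table A words the endpoint in terms of any adverse event. The treatment-emergent wording of the primary safety analysis comes from the protocol synopsis.

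A reader might infer that two programmers are bound to produce different counts, or that worsened events will be missed and risk understated. The documents support neither as a certainty. The first depends on which section a programmer follows, and the second on recording practice that the documents leave open.

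**Conclusion.** The Day 1 conflict is established from the text alone and needs no assumption about the data. The worsening gap is also in the text, but it has consequences only if a worsening is entered on the original record. The number of affected events is unknown. The effect on the overall TEAE proportion is probably small, and it may be more visible for individual preferred terms.

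The correction is worth making before the tables are run, because the rule feeds every TEAE table and the Day 1 part uses an item that SAP 6.2 says is collected. The documents do not support a claim that the main safety result is materially biased.

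The SAP also narrows the protocol exception to severity without saying so. Under Protocol 9.4 the SAP supersedes the protocol where they differ, so the causality and seriousness triggers would lapse without being listed as a change.

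**What to change.** 1. **SAP 16.1, known start date equal to the first-dose date:** use the eCRF item from 6.2. If it says the event began before intake, class it as pre-treatment. Otherwise, or if the item is missing, class it as a TEAE, in line with the worst-case principle in 15.1.
2. **SAP 15.1 and 16.1, worsening:** class a pre-treatment event as a TEAE if its severity increases on or after first dose and no later than 14 days after the last dose. State that this is identified from a new event record or from the dated change in severity. Add the exception to the exclusion sentence in 15.1.
3. **SAP 3.2:** either keep the protocol's triggers for increased causality and for meeting seriousness criteria, or list their removal as a change from the protocol.

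**Cost:** a few lines of text and of derivation code. The Day 1 change needs no new data. The worsening branch needs the date of the severity increase, and the documents do not show that this is collected within an event record. The sponsor should check the eCRF and its completion guidelines before finalising that part.
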